Furthermore, the lesion load in FLAIR in mm³ (reference MRI) is available only for 258 out of 316 patients (those for whom the MRI images could be retrieved). Moreover, obtaining this volume is not reliable because the software does not provide a sufficiently precise estimate. Therefore, no adjustment will be made for the lesion load, and the number of T2/FLAIR lesions on the reference MRI will be used instead as an indicator of lesion load (in 2 modalities: <9 lesions, >= 9 lesions).

In the event of the use of an incorrect stratum during randomization (randomization performed for the stratum with contrast enhancement on the diagnostic MRI while the true value was an absence of contrast enhancement, and vice versa), the analyses will be adjusted for the contrast enhancement value on the diagnostic MRI (Yelland et al., 2022). The stratum error rate will be described by arm.

Primary Analysis (Time to EDA)

Time to EDA is the duration between the date of the first administration of the experimental treatment and the date of EDA.

Date of EDA is:

- The date of the "conversion MRI" for patients with EDA determined by the appearance of NEL on MRI without having a relapse during the follow-up,

- The date of the first symptoms of a relapse for patients with EDA determined by a new relapse without the appearance of NEL on MRI during the follow-up,

- The earlier of the two dates between the date of the first symptoms and the date of the MRI showing NEL for patients who have both a relapse and NEL on MRI during the follow-up.

Patients lost to follow-up or not showing EDA during the follow-up will be right-censored at the date of the last news. The endpoint date will be established for each patient at the date of the end-of-study visit conducted 24 months (2 years) after inclusion.

Time to EDA in both arms will be graphically represented using the Kaplan-Meier method.

The proportional risk of EDA in the experimental arm compared to the placebo arm will be estimated along with its 95% confidence interval using a random-effects Cox model (random center effect) after checking the proportional hazards assumption. Adjustment will be made for the same variables as those used when analyzing the rate of EDA.

Secondary Analyses

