Reformulated Objective G2: Study the link between the occurence of EDA and vitamin D levels (25(OH)D2 and 25(OH)D3) during follow-up.

A mixed-effects regression model will be estimated. The model variables will include:

- Occurrence of EDA (relapse or MRI) (outcome variable)
- Treatment arm (adjustment variable)
- Center as a random effect (multiple patients per center)

- Patient as a random effect (multiple measurements per patient)

- Levels of 25(OH)D2 and 25(OH)D3 measured during follow-up (explanatory variables of interest)

- Visit (temporal chronological variable)

Objectives H, I, and J do not require statistical analyses and involve the establishment of biobanks.

Secondary Objective K: Estimate the discordance rate between the presence of NEL on follow-up MRI scans determined by the neurologist during the study and the result of the centralized MRI analysis performed at the end of the study (EDA not confirmed retrospectively or, conversely, detection of EDA not identified during the study). Additionally, estimate the rate of patients retrospectively identified as erroneously included based on centralized MRI reevaluation (inclusion criterion MRI not verified during centralized reading of the baseline MRI).

Discordance between decisions made during the study by neurologists and the results of centralized reevaluation analyses will be determined for each patient throughout his followup. The discordance rate will be estimated and presented with a 95% confidence interval.

The rate of patients retrospectively identified as erroneously included will also be estimated and presented with a 95% confidence interval.

Anticipated Level of Significance:

A difference will be considered statistically significant when the significance level of the test is less than or equal to 0.05.

Method for Handling Missing, Unused, or Invalid Data:

For the analysis of the primary outcome, if a patient is lost to follow-up without experiencing EDA, they will be considered as NEDA at the end of the 2-year follow-up and censored at the date of the last known status.

Regarding the adjustment variables in the primary analysis:

- If the gadolinium-enhancement status at the diagnostic MRI scan is unknown for a given patient, the missing data will be imputed by the gadolinium-enhancement status at the

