baseline MRI scan for that patient if known. If the latter is also missing, the gadoliniumenhancement status used as the randomization stratification variable will be employed.

- When the date of the CIS is missing, it will be extrapolated from the date of the diagnostic MRI scan plus the median time between the CIS and the diagnostic MRI scan.

If the number of T2/FLAIR lesions (used as an indicator of lesion burden, in two categories "<9 lesions " and " >= 9 lesions ") at the baseline MRI is missing, it will be analyzed in a third category "Number of Lesions Missing".

- If the EDSS score is missing at baseline, it will be imputed by the first non-missing EDSS scores at the M3 and M12 visits, subtracting the median of the EDSS score difference between M0 and M3 (respectively between M0 and M12) obtained from patients with scores recorded at both visits. If the result is negative, the median will not be subtracted.

For other secondary outcome measures, no method for imputing missing data is planned.

Analysis population:

Patients who did not receive the study treatment will not be considered in the analyses, which will be conducted on a modified intention-to-treat basis.

All patients who received at least one dose of the study treatment will be included in the analyses.

Thus, the following individuals will not be considered in the analyses:

- Patients with "Study discontinuation at the investigator's decision due to disease activity identified on the baseline MRI" or occurrence of a relapse before treatment onset.

- Patients who withdrew their consent.

- Patients who did not undergo a baseline MRI (withdrawal of consent, inability to undergo MRI).

- Patients lost to follow-up immediately after inclusion (at the inclusion visit and/or baseline MRI), with no follow-up data.

- Patients mistakenly included without MS or with occurrence of a relapse before the baseline MRI.

These patients cannot be included in an intention-to-treat analysis because they have no follow-up and, therefore, no information on disease activity during follow-up.

Bibliographic References

Edgar et al 2021 : Including random centre effects in design, analysis and presentation of multi-centre trials. Trials. 2021, 22:357.

Kahan 2014 : Accounting for centre-effects in multicentre trials with a binary outcome – when, why, and how? BMC Medical Research Methodology, 2014, 14:20.

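### Secondary Objective K's erroneous-inclusion rate is decided on the baseline MRI, yet the modified-ITT rule removes untreated patients from it because they lack follow-up that the rate does not need

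*SAP*

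**What the plan says.** Secondary Objective K has two estimates. The first is the discordance between the neurologists' reading of new or enlarging lesions on follow-up MRI and the central reading; it "will be determined for each patient throughout his followup". The second is the share of patients included in error, defined as "inclusion criterion MRI not verified during centralized reading of the baseline MRI". For the second the SAP says only: "The rate of patients retrospectively identified as erroneously included will also be estimated and presented with a 95% confidence interval". No denominator is given for either.

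The Analysis population section sets one rule for everything: "Patients who did not receive the study treatment will not be considered in the analyses, which will be conducted on a modified intention-to-treat basis". It adds: "All patients who received at least one dose of the study treatment will be included in the analyses". It then lists the groups that drop out as a result. They include patients stopped by the investigator for activity on the baseline MRI, and "Patients mistakenly included without MS or with occurrence of a relapse before the baseline MRI". The reason given is that these patients have no follow-up and so no information on later disease activity.

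Under Primary Analysis (Rate of EDA), FLAIR lesion load on the reference MRI is reported as "available only for 258 out of 316 patients (those for whom the MRI images could be retrieved". The missing-data section plans no imputation for secondary outcomes.

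**The concern.** The reason for the exclusions fits outcomes observed after treatment starts. It does not fit a quantity settled by the baseline scan. A patient who was randomised, had a baseline MRI and was never treated can still be classified as correctly or erroneously included if that scan was read centrally. As written, the plan removes such patients from a rate meant to measure inclusion errors, and some of them left the trial because they were recognised as mistakenly included.

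At stake is what the rate and its 95% confidence interval describe. A reader will take them as the error rate among everyone the centres included, whereas the plan yields the rate among those who went on to receive a dose. If the two groups differ, the interval does not show it. It also does not show the uncertainty from baseline scans that could not be read centrally.

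**Working it through.** The SAP states no figure for this rate, so there is none to reproduce. The check has two parts.

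**1. Effect of the modified-ITT rule**

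Let x of n kept patients fail the MRI criterion at central reading, and m of e dropped patients fail it.

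- Rate under the plan: x/n.
- Rate in all included patients: (x + m)/(n + e).
- The plan's rate is too low exactly when m/e > x/n, and too high when m/e < x/n.

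The SAP gives none of x, m or e. Assume n = 316 kept, x = 16 and e = 10. The plan's rate is then 16/316 = 5.1%.

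| Dropped patients who fail (m of 10) | Rate in all included | Plan's 5.1% is |
|---|---|---|
| 0 | 16/326 = 4.9% | slightly too high |
| 2 | 18/326 = 5.5% | too low |
| 5 | 21/326 = 6.4% | too low |

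The direction depends on the dropped patients, about whom the SAP gives no figures.

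**2. Effect of unread baseline scans**

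Inputs: 258 of 316 patients with retrieved reference-MRI images. Two assumptions are made: the reference MRI is the baseline MRI of Objective K, and an image that was not retrieved was not read centrally.

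- Retrieved: 258/316 = 81.6%. Not retrieved: 316 − 258 = 58, and 58/316 = 18.4%.
- With f failures among the 258, the lower bound over 316 is f/316 (none of the 58 fail) and the upper bound is (f + 58)/316 (all fail).

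| Assumed failures f | f/258 | Lower bound f/316 | Upper bound (f + 58)/316 |
|---|---|---|---|
| 5 | 1.9% | 1.6% | 63/316 = 19.9% |
| 13 | 5.0% | 4.1% | 71/316 = 22.5% |
| 26 | 10.1% | 8.2% | 84/316 = 26.6% |
| 52 | 20.2% | 16.5% | 110/316 = 34.8% |

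The bounds are always 18.4 points apart. For f = 13 the exact (Clopper-Pearson) 95% interval on 258 is 2.7% to 8.5%, which conveys none of that spread.

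Using read patients as the denominator does not fix the direction of bias either. With 13/258 = 5.0%, the estimate is 0.9 points too high if the 58 fail at 0%, about right if they fail at 5%, and 0.9 points too low if they fail at 10%.

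**The case against.** The strongest reply is that the two groups are different. Objective K counts failure of the MRI criterion at central reading. The Analysis population section drops untreated patients who turned out not to have MS, relapsed early, or left for other reasons. A treated patient who fails at central reading stays in under the one-dose rule, so the rate is not emptied by construction. Nor does the SAP say that activity on the baseline MRI means the inclusion criterion was unmet. All of this stands. Overlap between the groups is possible but not shown.

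A reader might go further and infer that both Objective K rates are biased low. The documents do not support that, for four reasons:

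- For the inclusion-error rate the direction is open, as the working shows.
- Dilution by the 58 patients would require counting unread patients as correct or concordant. The SAP contains no such rule and plans no imputation for secondary outcomes.
- The 258 of 316 figure is given for the reference MRI. The SAP gives no retrieval figure for the follow-up scans on which discordance is judged.
- Dropped patients have no follow-up to compare, so leaving them out does not bias discordance.

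It can also be said that this is a descriptive objective with no hypothesis test. That stands too, and it limits the weight of the point.

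The reply does not answer one thing: the stated reason for the exclusions is lack of follow-up, and this rate needs none.

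**Conclusion.** The point holds in a limited form and is minor. Read as written, the modified-ITT rule covers a rate to which its justification does not apply. The rate therefore describes treated patients rather than all those included, and it may be biased in either direction. It is too low only if the dropped patients fail the MRI criterion more often than those kept.

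The size cannot be fixed from the SAP. In the illustration the shift runs from −0.2 to +1.4 points (4.9% to 6.4%, against 5.1%), and it rests on assumed counts. The uncertainty from unread baseline scans is larger: 18.4 points between best and worst case, if 258 of 316 is the share read centrally. The SAP does not say whether 316 is all randomised patients or the modified-ITT set. The first illustration takes it as the kept set; if it is all randomised patients, the counts change but the condition for the direction does not.

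The discordance rate and the primary test are not affected by the exclusions.

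**What to change.** Add to the Analysis population section an exception for the erroneous-inclusion rate of Objective K only:

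- Estimate it in all randomised patients whose baseline MRI was read centrally, treated or not, including those dropped as mistakenly included. Give the modified-ITT rate alongside.
- Use patients with a central reading of the baseline MRI as the denominator. Report the number unread by arm, and give best-case and worst-case bounds for them.
- Keep the modified-ITT set for the discordance rate, and state that its denominator is patients with both a local and a central reading.

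The cost is a few lines of SAP text and one extra row in a table; no new data collection is asked for. The limit is that the change uses only central readings that already exist, and the SAP does not say whether they exist for untreated patients. If they do not, these patients appear in the count of unread scans and in the bounds, which is still more informative than leaving them out without comment.

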Patients lost to follow-up before experiencing EDA will be considered as not having had the event. A sensitivity analysis with the maximum bias assumption will be conducted by considering missing data (discontinuation of follow-up before the end of the 2-year follow-up with NEDA) in the interventional arm as failures (non-responders = EDA) and those in the control arm as successes (responders = NEDA).

The rate of EDA in both arms will be estimated and then compared between the two treatment arms using mixed-effects logistic regression (random center effect). The treatment arm will be the factor of interest in the model. Adjustment will be made for randomization stratification factors (center, contrast enhancement on diagnostic brain and spinal cord MRI), known prognostic factors listed in section 4.1.4 of the protocol (Age, Gender, Presence of contrast enhancement on the reference MRI, Lesion load in FLAIR in mm³, Number of lesions with contrast enhancement on the reference MRI, EDSS score at baseline), and the time between CIS and the first administration of the treatment, which varies among patients (from a few days to 95 days = maximum of 90 days between CIS and the reference MRI and the first administration of the study treatment, which takes place on the first Saturday post-MRI). Adjustment for the center effect will be performed by considering the center as a random effect in the model (Kahan 2014, Kahan et al. 2015, Edgar et al. 2021).

The number of lesions with contrast enhancement on the reference MRI could not be determined quantitatively. This information is provided by recording the presence of contrast enhancement with a precision level in 3 modalities (similar to the diagnostic MRI): no lesions with contrast enhancement, one lesion with contrast enhancement, and at least two lesions with contrast enhancement. This information will be used as an adjusting variable only if it is not significantly associated with contrast enhancement on the diagnostic MRI (a randomization stratification factor), for which an adjustment is performed. The statistical significance of the association will be assessed using the Chi-square test or Fisher's exact test if the Chi-square test is not applicable, with a significance level set at < 0.05.

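### The rule for a missing CIS date adds the median CIS-to-MRI interval where it should subtract it, so the imputed onset falls after its own diagnostic scan

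*SAP*

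**What the plan says.** The section on missing, unused or invalid data has a list introduced by "Regarding the adjustment variables in the primary analysis". One item in it covers a missing CIS date, which is to be "extrapolated from the date of the diagnostic MRI scan plus the median time between the CIS and the diagnostic MRI scan".

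The CIS date matters because the section on the rate of EDA adjusts the mixed-effects logistic model for "the time between CIS and the first administration of the treatment, which varies among patients". That section gives the range of this variable as "from a few days to 95 days = maximum of 90 days between CIS and the reference MRI", followed by the wait until the first Saturday after that scan.

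The section on time to EDA carries the variable into the Cox model: "Adjustment will be made for the same variables as those used when analyzing the rate of EDA". The survival time itself does not use the CIS date: "Time to EDA is the duration between the date of the first administration of the experimental treatment and the date of EDA".

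**The concern.** The diagnostic MRI is part of the work-up of the CIS, so it comes after the onset. The SAP does not state this order; it is inferred from the name of the scan. Given that order, the onset is recovered by going back in time from the scan. The rule goes forward, which dates the first symptoms after the scan made to explain them.

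This is not a choice between two defensible imputations. For a positive median interval, the written rule is further from the truth than using the scan date with no offset. It is also fixed in advance for a covariate of both primary models. Coded literally, it gives impossible dates. Coded sensibly, the analysis departs from its own plan without a record.

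**Working it through.** **Inputs**

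- From the SAP: the imputation rule, the definition of the covariate, its stated range, and the 316 patients mentioned where FLAIR lesion load is discussed.
- Not in the SAP, so assumed below: m, the median time in days from CIS to diagnostic MRI (m > 0); d, a patient's true CIS-to-MRI time (d ≥ 0); t, the days from diagnostic MRI to first dose; and the number of missing CIS dates.

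**The plan's own figure.** The 95-day maximum reproduces as 90 days from CIS to reference MRI plus 5 days from a Monday scan to the next Saturday: 90 + 5 = 95. This concerns the reference MRI, so it does not prove when the diagnostic MRI took place. It does show that the SAP counts an interval between the CIS and a later event forward, as a positive number.

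**A neighbouring rule.** In the same list, a missing baseline EDSS is rebuilt from a later visit by subtracting the median change from baseline to that visit. That is the same operation, an earlier value recovered from a later one, with the opposite sign to the CIS rule.

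**Difference between the two signs**

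- As written: CIS = MRI + m, so the covariate is t − m.
- With minus: CIS = MRI − m, so the covariate is t + m.
- Difference: (t + m) − (t − m) = 2m.

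For m = 2, 5, 10, 20 and 30 this is 4, 10, 20, 40 and 60 days.

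**Error against the true date.** The true CIS is MRI − d. The error is m + d as written, |m − d| with minus, and d with no offset. For m = 10:

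| d (days) | As written | Minus | No offset |
|---|---|---|---|
| 5 | 15 | 5 | 5 |
| 10 | 20 | 0 | 10 |
| 20 | 30 | 10 | 20 |

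The written rule is m days worse than no offset in every row, since (m + d) − d = m.

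**Values outside the stated range.** As written, the covariate is zero or negative when t ≤ m. For t = 20:

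| m (days) | As written (t − m) | Minus (t + m) |
|---|---|---|
| 10 | 10 | 30 |
| 20 | 0 | 40 |
| 30 | −10 | 50 |

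**Effect on the arm estimate.** All inputs except the 316 patients are assumed: 1:1 arms, arm log odds ratio −0.5, covariate slope −0.01 per day, d gamma-distributed with median about m, t uniform from 5 to 60 days, and a logistic model with arm and covariate only. There were 1,000 runs per setting. The table gives the 95th percentile of the absolute change in the arm log odds ratio between plus and minus:

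| Missing CIS dates | m = 10 | m = 30 |
|---|---|---|
| 1% (about 3 patients) | 0.007 | 0.015 |
| 5% (about 16) | 0.014 | 0.034 |
| 10% (about 32) | 0.018 | 0.041 |

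The mean standard error was 0.23. A repeat with gamma shape 2 gave 0.006 to 0.042. The median change in that repeat was 0.012 in the most extreme setting, 10% missing with m = 30.

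**The case against.** The strongest reply is that this is a one-word slip with no shown effect on any conclusion. It touches one adjustment variable, only in patients whose CIS date is missing, and that number may be zero. The rule is the same in both arms and enters neither the event definition nor the survival time. The largest simulated shift needs both 10% missing and m = 30, and typical shifts are smaller. The simulation also leaves out the centre effect and the other adjusters, and with m = 30 it lets some patients exceed the 95-day limit. All of this stands. It limits the harm but does not make the rule right.

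A second reply is that plus would be correct if the median were held as a negative number, CIS date minus MRI date. The SAP does not say so. Its wording, "the median time between the CIS and the diagnostic MRI scan", reads as a duration, and it uses similar wording elsewhere for forward, positive intervals. This reply does not stand.

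A third is that a date check is redundant once a positive median is subtracted. That is true of the check that the CIS does not fall after the scan, provided the code is right. A check against the stated range still has a use, because subtraction can overshoot: assumed t = 70 and m = 30 give 100 days, above the 95-day limit.

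**Conclusion.** The rule is wrong as written and should be corrected. For any positive median interval it dates the imputed CIS after its own diagnostic scan, shortens the covariate by 2m days relative to the correctly signed rule, and does worse than applying no offset. This rests on the diagnostic MRI following the CIS and on the median being a positive duration.

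The size in days cannot be fixed from the SAP, because m and the number of affected patients are not given. The consequence for the treatment comparison is probably small: under the assumptions above, at most about 0.04 on the log odds ratio scale in 95% of runs, or less than a fifth of the standard error (0.041 / 0.23 ≈ 0.18). It deserves correction because it is a definite error in a prespecified rule for the primary analysis, not because it is likely to change the result.

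**What to change.** In the missing-data section, replace plus with minus, so that the imputed CIS date is the diagnostic MRI date minus the median CIS-to-MRI time. State that this median is a positive number of days.

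Check that no imputed CIS date is later than the diagnostic MRI, and compare the resulting time to first dose with the stated range of a few days to 95 days. Report by arm how many CIS dates were imputed; this is good practice rather than part of the correction, and it lets a reader see how far the rule reaches.

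The cost is one word in the SAP, one sign in the code if it follows the text, one date check and one line in a table.

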Secondary Objective A: Evaluate clinical efficacy on the number of relapses during the study period. The determination of the number of relapses is based on data from the EDA visit and the summary table of relapses based on the evaluation at Month 24. The number of relapses will be compared between the two arms using a non-parametric Mann-Whitney Wilcoxon test.

Secondary Objective B1: Describe the parameters of magnetic resonance imaging (brain and spinal cord MRI) at the "conversion MRI":

- Appearance of NEL on brain MRI in T2/FLAIR (including size increase) and/or on spinal cord MRI in T2 ("conversion MRI" Yes/No)

- New brain or spinal cord gadolinium-enhancing T1 lesions (active lesion(s) Yes/No)

- Lesion load in mm³ of each brain MRI from the FLAIR sequence

- Total number of gadolinium-enhancing T1 lesions (categorical measure: none, one, at least two)

Secondary Objective B2: Describe the magnetic resonance imaging (brain and spinal cord MRI) parameters during follow-up:

Normalized brain volume obtained from the 3D T1 sequence at different visits
Change in global brain volume (mm3, from the 3D T1 sequence) between the baseline examination and the 2-year examination on one hand, and between the 3-month examination and the 2-year examination on the other hand, to limit the effect of pseudo-atrophy after the first relapse

Secondary Objective C: Evaluate efficacy on disability progression, measured by the EDSS score and Kurtzke functional scores (Kurtzke 1983; Noseworthy et al. 1990; Goodkin et al. 1992) at baseline and during follow-up, then considering scores at M0 and M24 only.

Secondary Objective D: Evaluate efficacy on cognitive abilities (PASAT) (Cutter et al. 1999; Fischer et al. 1999; Parmenter et al. 2006) at baseline and during follow-up, then considering scores at M0 and M24 only.

Secondary Objective E: Evaluate efficacy on quality of life (EQ5D, SF36, TLS-QoL10, and TLS-COPING10 questionnaires), fatigue (FSMC questionnaire), and anxiety/depression (HADS questionnaire) at baseline and during follow-up, then considering scores at M0 and M24 only.

For Objectives C, D, and E:

- A first mixed-effects regression model will be used to compare the evolution of the outcome measures (EDSS score for Objective C, PASAT score for Objective D, and quality of life scores for Objective E). The model variables will include:
 - Scores at different visits (outcome variables)

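### A missing baseline EDSS is filled from M3 or M12 scores, so post-randomisation information enters a covariate of both primary models

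*SAP*

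**What the plan says.** Under Primary Analysis (Rate of EDA), the SAP's list of prognostic covariates for the mixed logistic model ends with "Number of lesions with contrast enhancement on the reference MRI, EDSS score at baseline". For the Cox model, Primary Analysis (Time to EDA) adds: "Adjustment will be made for the same variables as those used when analyzing the rate of EDA". Baseline EDSS is therefore in both primary models.

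The section Method for Handling Missing, Unused, or Invalid Data opens its covariate rules with "Regarding the adjustment variables in the primary analysis". For a missing baseline EDSS it then states that "it will be imputed by the first non-missing EDSS scores at the M3 and M12 visits". The follow-up score is corrected by one median change, M0 to M3 or M0 to M12 according to the visit used. That median comes from patients with both scores; no split by arm or relapse status is mentioned. An exception follows: "If the result is negative, the median will not be subtracted".

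Two other places fix what these follow-up scores are:

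- Time zero for the primary outcome is the first dose: "Time to EDA is the duration between the date of the first administration of the experimental treatment and the date of EDA".
- Secondary Objective C is to "Evaluate efficacy on disability progression, measured by the EDSS score", so follow-up EDSS is an efficacy outcome.

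**The concern.** Covariate adjustment in a randomised trial is safe because a baseline covariate cannot be affected by the assigned treatment or by what happens afterwards. A score taken at M3 or M12 lacks that protection. It may carry a treatment effect on disability, and it may carry the residue of a relapse, which is one of the two ways a patient can have EDA. Used as a baseline value, it lets the model predict the event partly from its consequences. In the Cox model, an M12 score would be treated as known at first dose and used to explain hazards up to a year before it was measured.

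At stake are the meaning of the EDSS coefficient and, to a lesser degree, the treatment estimate in the trial's main analysis.

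**Working it through.** **Step 1: timing and dependence.** The SAP places the pieces as follows.

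| Item | SAP section | Consequence |
|---|---|---|
| EDSS at baseline is a covariate | Primary Analysis (Rate of EDA and Time to EDA) | The fill enters both primary models |
| Follow-up time starts at first dose | Primary Analysis (Time to EDA) | M3 and M12 are on-study, post-dose visits |
| EDA is relapse and/or new or enlarging lesions within two years | Primary Analysis (Rate of EDA) | M3 and M12 lie inside the outcome window |
| EDSS is compared between arms | Secondary Objective C | The filling score is an efficacy outcome |
| The EDSS models include an arm-by-relapse interaction | Models for Objectives C, D and E | The SAP itself allows scores to differ with relapse |

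The other covariate rules in the missing-data section use the diagnostic or baseline MRI, the recorded stratum or a missing category. Only the EDSS rule uses follow-up data.

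**Step 2: does the median subtraction repair it?** Filled value = follow-up EDSS − median change. A median over all patients removes a typical shift. It barely responds to a minority who relapse, and it is the same number for everyone. In every scenario of the large simulation below, the pooled median change was 0.0, so the subtraction removed nothing.

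**Step 3: size.** The SAP gives no figure to reproduce and does not state how many baseline scores are missing. All inputs below except n = 316 are assumptions.

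*Trial-size simulation* (n = 316, arm log-OR −0.6, 40% of EDA patients with EDSS raised by 1, direct treatment effect on EDSS −0.2, 1,500 replicates per level):

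| Missing | Shift in arm log-OR (toward zero) | EDSS coefficient (about 0.30 with full data) |
|---|---|---|
| 5% | 0.002 | 0.31 |
| 10% | 0.005 | 0.34 |
| 20% | 0.010 | 0.37 |

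Filling with the M0 mean moved the arm log-OR by at most 0.002.

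*Large-sample simulation* (3 × 400,000 patients per scenario; logistic model with arm and EDSS only; 1:1 allocation; about 62% EDA in control at mean EDSS; EDSS log-OR 0.2 per point; 12% of EDA patients relapsing before M3 or 35% before M12; missing at random). For M12 fill with a 2-point relapse jump and no direct treatment effect on EDSS:

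| Missing | OR, true baseline | OR, SAP rule | OR, baseline median | EDSS coefficient, true → SAP rule |
|---|---|---|---|---|
| 2% | 0.6006 | 0.6004 | 0.6007 | 0.199 → 0.211 |
| 10% | 0.6011 | 0.6006 | 0.6013 | 0.197 → 0.254 |
| 20% | 0.5990 | 0.5974 | 0.5995 | 0.201 → 0.309 |
| 50% | 0.5994 | 0.5965 | 0.6006 | 0.201 → 0.432 |

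With M3 fill and the same jump, the coefficient under the SAP rule was 0.204, 0.220, 0.231 and 0.277 at the same missing shares.

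With a true OR near 1 and a direct treatment effect on EDSS of −0.3 (M12 fill):

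- 10% missing: 1.0021 → 1.0083, ln(1.0083/1.0021) = 0.006.
- 50% missing: 1.0031 → 1.0585, ln(1.0585/1.0031) = 0.054.

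A further large-sample check, at up to 20% missing, moved the arm log-OR by no more than about 0.014. With 10% missing and 35% of EDA patients raised by 2 points, it moved the EDSS coefficient from about 0.30 to 0.34.

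**Step 4: scale.** With 158 per arm (316/2, assuming equal allocation), the unadjusted log-OR standard error is √(2/(158 × p(1−p))). It is smallest at p = 0.5: √(2/(158 × 0.25)) = 0.225. So 0.002 is about 1% of a standard error (0.002/0.225), and 0.014 about 6% (0.014/0.225).

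**The case against.** The strongest reply is that the harm to the treatment estimate is negligible, and most of that reply stands.

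- **Size.** Shifts of 0.002 to 0.014 in log-OR are lost in a standard error of at least 0.22. Treatment arm is the factor of interest; the EDSS coefficient is a nuisance parameter. This stands.
- **Direction.** A reader might infer that the rule generally conditions away part of the treatment effect. The SAP does not support that. A shift toward zero needs an assumed direct effect of treatment on EDSS. Without one, the OR moved by at most 0.0005 at 10% missing or less, and at 50% it moved slightly away from the null (0.5994 to 0.5965).
- **Timing.** M3 is used before M12, and EDA includes MRI-only events that need not change EDSS. Not every patient with early EDA gets an inflated baseline. With 12% of EDA patients raised by 1 point, 10% missing and a direct effect of −0.2, the EDSS coefficient moved only from 0.301 to 0.306.
- **Benefit.** The rule keeps the patient's own correlated score, so it is wrong to say it offers nothing. With the same 12%, 1 point and 10% missing but no direct effect, the arm log-OR was −0.5981 with the true baseline, −0.5981 under the SAP rule and −0.5969 with mean fill.
- **Negative-value exception.** A reader might infer that a lower follow-up score can give a higher filled baseline. That is possible: with a median worsening of 1.5, a score of 1.5 becomes 0 while 1.0 stays 1.0. But on EDSS steps 0, 1, 1.5, 2 and so on (assumed), medians of 0.5 and 1.0 keep the order. Reversal appeared only above 1 point, and the SAP gives no median to suggest that.

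What the reply does not answer is the principle: the covariate can depend on arm and outcome, and a baseline-only fill avoids this at almost no cost.

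**Conclusion.** The point holds as a flaw in a pre-specified rule of the primary analysis. It does not show that the trial's result is materially biased. A value labelled baseline is taken from post-dose scores that relapse and treatment can both move, and the median correction does not undo this.

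The clearest consequence is an inflated EDSS coefficient when relapses raise EDSS. The arm estimate is distorted only slightly, mainly if treatment acts directly on EDSS: about 0.002 to 0.014 in log-OR at 5% to 20% missing. The problem grows with the missing share and with use of M12 rather than M3.

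These sizes depend on assumed relapse shares, EDSS jumps, treatment effects and missing shares, none of which is in the SAP. The simulations were logistic; the centre effect and the Cox model were not simulated. If very few baseline scores are missing, the numerical effect will be close to nil.

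A reader might also infer that the filled value serves as the M0 score in the Objective C model. The SAP does not say so: the rule is confined to primary-analysis covariates, and no imputation is planned for other secondary outcome measures.

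**What to change.** Replace the M3/M12 rule and its negative-value exception with a fill from baseline data only, pooled over arms: the M0 mean or median, optionally with a missing indicator. A bare missing category, as used for the lesion count, is less suitable because the SAP treats EDSS as quantitative under Objective G1. Report the number of imputed baseline EDSS scores by arm. Keep the M3/M12 fill at most as a sensitivity analysis.

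The change also closes a gap: the present rule gives no value for a treated patient with neither an M3 nor an M12 score, although all treated patients are to be analysed.

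The cost is SAP wording and a little covariate precision, because the imputed patients' own follow-up scores are no longer used. In the large-sample simulation the baseline-median fill kept the treatment OR within about 0.002 of the true-covariate result in every scenario.
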